4.5 Assessing the Design and its Implications

One way of assessing this research design is to ask whether, and how well, it avoids the twin dangers of producing a 'false negative'⁵⁷ (such as claiming that the initiative has no impact when it has) or a 'false positive'⁵⁸ (such as claiming the initiative has an impact when it has not). That question has also guided the research design.

It could be argued that, in an exploratory initiative such as this, the risk of a false negative could have more serious consequences than a false positive. This is because a false negative may close off the possibility of finding more effective interventions for children and their parents⁵⁹, similar to the scenario in scientific research where a false negative may close off valuable lines of further inquiry⁶⁰. At the same time, the danger of false positives should not be underestimated, and may indeed be the more usual scenario, since some programmes claiming to have a positive impact could turn out to be 'false positives' if a scientific evaluation were ever carried out⁶¹.

57 A false negative is the term used to refer to a finding that is thought to be not-statistically-significant when it is, also referred to as Type I error.

58 A false positive is the term used to refer to a finding that is wrongly thought to be statistically significant, also referred to as Type II error.

59 This risk was also highlighted by the authors of the first impact report on Sure Start Programme: 'readers of this report need to appreciate the critical distinction between evaluations reporting (1) no evidence of effectiveness and (2) the lack of effectiveness. That is, a conclusion that "no evidence of effectiveness could be detected", is distinctly different from concluding that the programme is ineffective in realizing its goals of enhancing child development and family functioning. In other words, absence of evidence (of effectiveness) is not evidence of absence of effectiveness. The critical distinction is between detecting evidence of effectiveness and lack of effectiveness. This distinction is particularly important for this report as it focuses on an intervention that is not necessarily well established in many places for children and families who have not been studied repeatedly over time.' (National Evaluation of Sure Start Team, 2005a:3).

60 The eminent child psychologist and founder of the bioecological model of human development, Urie Bronfenbrenner (1917-2005), also observed that, from the scientific perspective of discovery rather than verification, 'Type I errors can entail an even greater risk than errors of Type II' because 'dismissing as invalid a finding that points the way to a fuller and more precise explanation for the phenomenon under investigation may result in a greater loss than that produced by accepting a finding that is highly significant because of as yet undifferentiated and thereby confounded factors producing the phenomenon in question (e.g., the failure to distinguish Process from Context). The greater risk in the discovery process of dismissing findings as Type 1 errors is further compounded by the phenomenon of magnification of early environmental differences over time' (Bronfenbrenner and Morris, 2006:802).

61 For example, the Controller and Auditor General examined programmes in the area of educational disadvantage and, based on a desk-top review of the available evidence, noted the apparent lack of positive impact. This was based on a review of the Educational Disadvantage Initiatives in the Primary Sector between 1984 and 2004 which involved an expenditure of €62 million in the school year 2003/4. The review revealed that reading standards in designated disadvantaged schools - the only indicator for which there is consistent data over the period - deteriorated in the period between 1984 and 2004: 'In both 1998 and 2004, pupils in designated disadvantaged schools had significantly lower average scores than pupils in non-designated schools with a slightly bigger gap in 2004 than in 1998. The data suggest a slight drop in reading standards of pupils in designated disadvantaged schools between 1998 and 2004.' (Controller and Auditor General, 2006, p.51). Reviews of other programmes undertaken by the Controller and Auditor General, such as regeneration of Ballymun at a cost of €942 million, suggest that the impact may never be known due to 'the lack of baseline statistics and inadequate and variable information feedback on programmes. In future regeneration programmes, the Department should ensure that the baseline position is established and that there is regular monitoring of key outcomes' (Controller and Auditor General, 2007, p.11)

The need to minimise the risk of false negatives and false positives has shaped the entire research design, but has been particularly influential in shaping three aspects of the evaluation. First, the focus of the evaluation is exclusively on interventions which are *substantial and sustained*. The definition of what constitutes a *substantial and sustained* intervention is left to each individual project based on their judgement that the intervention is capable of producing a measurable impact on children and/or their parents, or indirectly on staff. This requirement may have been taken into account already during the selection of projects but is mentioned here as a core evaluation requirement since interventions which are not *substantial and sustained* are unlikely to produce a measurable impact. This follows logically from the fact that the best programmes for children and their parents tend to produce relatively small effects. These are typically expressed in terms of 'effect sizes' which is a simple way of standardising and comparing the difference between the treatment group and the comparison group (see Appendix One)⁶². For example, childcare programmes like High Scope⁶³, Early Head Start⁶⁴, Effective Pre-School and Primary Education Project⁶⁵, all have small effects. The same applies to family support programmes like Sure Start⁶⁶ and Springboard⁶⁷. None of this implies that small effects are not worthwhile⁶⁸; only that

62 The formula involves subtracting the mean at baseline from the mean at follow-up and dividing by their pooled standard deviation. The convention, referred to as 'Cohen's d', is that a coefficient between 0.2 and 0.5 indicates a small effect, between 0.5 and 0.8 indicates a moderate effect, and above 0.8 indicates a large effect (Cohen, 1992; Van Belle, 2002:31). As an example, an effect size of 0.8 means that the score of the average person at follow-up is 0.8 standard deviations above the average person at baseline, and hence exceeds 79% of the baseline scores. Unlike statistical significance, the effect size statistic is independent of the group size and therefore considered more informative and meaningful. The Centre for the Study and Prevention of Violence at University of Colorado in Boulder, USA which selects 'Blueprints Model Programs' on the basis of 'the most rigorous tests of effectiveness in the field', requires that all Blueprint programmes have 'at least moderate effect sizes' (<http://www.colorado.edu/cspv/blueprints>). The Promising Practices Network run by the Rand Corporation defines a programme as 'proven' where, inter alia, 'at least one outcome is changed by 20%, 0.25 standard deviations or more' which implies impacts at lower threshold of effects (<http://www.promisingpractices.net>) (see also Shonkoff and Phillips, 2000:342-343).

63 The overall effect size of the High Scope Perry Pre-School Programme in the US when participants reached the age of 23 was 0.36 (Schweinhart and Weikhart, 1997; Schweinhart, 2004; Schweinhart, Montie, Xiang, Barnett, Belfield, Nores, 2005). At age 14, reading and math scores improved by 0.33 standard deviations, a very significant achievement given that the US achievement gap in reading and math gaps between low-income and middle-income children at kindergarten entry is about 0.50 standard deviations (Barnett, 2011: 975).

64 The evaluation of Early Head Start found that 'overall impacts were modest, with effect sizes in the 10 to 20 percent range, although impacts were considerably larger for some subgroups, with some effect sizes in the 20 to 50 percent range. The overall pattern of favorable impacts is promising, particularly since some of the outcomes that the programs improved are important predictors of later school achievement and family functioning' (Mathematica Policy Research, 2002:xxv).

65 The effect size of high quality pre-school for children at the age of 11, according to the Effective Pre-School and Primary Education Project, was: 0.23 for pro-social behaviour, 0.25 for self-regulation, 0.29 for English, 0.34 for Mathematics, (Sammons, 2010:128-130).

66 The effect size of Sure Start when children were five years old, was 0.12 for Body Mass Index and 0.10 for physical health; for parents, it was 0.24 for harsh discipline, 0.29 for chaos in the home and 0.27 for home learning environment (National Evaluation of Sure Start Team, 2010:29).

67 The effect size of Springboard on children's strengths and difficulties was 0.30; for parents, its was 0.23 for communication between parent and child (McKeown, Haase and McKeown, 2006).

interventions which are 'light' in their design, intensity and duration are less likely to show a measurable effect.

Second, the overall envelope of resources for the evaluation enables the two core questions to be answered through a sample of 35 children and their parents in each project, in both the treatment and comparison groups, assessed at baseline and follow-up. This yields a total sample of 385 each in the treatment and comparison groups, and a combined sample of 770. As explained below, this sample size is adequate for the evaluation but is also close to the minimum required. For this reason, and in order to minimise the amount of extraneous variation within the sample, it was decided to confine the sample to one age-cohort of children (3.5 years and over) in order to maximise the possibility of finding an impact where there is one (a true positive) and being confident that if no impact is found it is also genuine (a true negative). Conversely, we avoided the risk of splitting the sample into two age-cohorts of children (such as 0.5 to 3.5 / 3.5 and over) since this would run the risk of producing inconclusive results because the resulting sample would lack the power to draw any statistically-significant conclusions about either age-cohort. The fact that there is near-universal uptake of childcare services for children in this age-cohort (3.5 years and over)⁶⁹ has the added benefit that there is relatively little self-selection in this population and therefore fewer of the methodological problems normally associated with programme evaluations, like this, which are based on a quasi-experimental method.

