9.2 Follow-up Data Analysis

The follow-up data analysis will involve the following components.

9.2.1 Repeat the analysis described in paragraphs 9.1.2, 9.1.3 and 9.1.4 above. This is necessary in order to make sure that, when baseline and follow-up data are merged, the latent variables underpinning the measurement and structural models are based on identical structure matrices and measurement scales. That is the only way of making valid comparisons between baseline and follow-up when using multi-dimensional outcome measures. This step will involve a recalibration of all latent concepts using the combined dataset since, only when these conditions are satisfied, will we be able to present robust ‘before-and-after’ comparisons of outcomes. The adjusted models of child, parent and staff outcomes will be presented graphically along with an interpretation of their meaning and implications.

9.2.2 Having established consistent and robust measurements for all multi-dimensional outcomes relating to children, parents and staff, we will present results on impact by comparing the difference between baseline and follow-up scores. Improvements in outcomes will be expressed in terms of a comparison of means, standard deviations and effect sizes. As explained earlier, the use of effect sizes is a simple way of standardising and comparing two sets of scores and allows the impact of NEYAI to be measured in a way that is comparable to other early years programmes. Table 3 is a draft of the format that will be used to present this data.

Table 3 Format for Presenting Effect Size Scores in the Final Report

Vari- able	Effect Size Score for Treatment Group (TG)												Effect Size Score for Comparison Group (CG)										
	BC	CC	CK	CN	DD	DL	FL	LD	LK	RO	TT	All	1	2	3	4	5	6	7	9	10	All	
*																							
**																							

*Denotes a statistically significant difference between treatment group and comparison group for that variable.

**Denotes a statistically significant difference between treatment group or comparison group and the GUI for that variable.

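### Footnote 62 and Table 3 scale each effect size by its own column's standard deviation, so columns with different spread cannot safely be compared or ranked in size

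*Protocol*

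**What the plan says.** Two places in the protocol describe the effect size, and they differ.

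- **Section 4.5, main text:** it is "a simple way of standardising and comparing the difference between the treatment group and the comparison group".
- **Section 4.5, footnote 62, attached to that text:** "The formula involves subtracting the mean at baseline from the mean at follow-up and dividing by their pooled standard deviation". The worked example reads an effect of 0.8 as a follow-up average that "hence exceeds 79% of the baseline scores". This is a within-group change, and "dividing by their pooled standard deviation" scales it by the spread of that group's own two waves.

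Section 9.2.2 sets out how results on impact are presented: "Improvements in outcomes will be expressed in terms of a comparison of means, standard deviations and effect sizes". It then points back: "As explained earlier, the use of effect sizes is a simple way of standardising and comparing two sets of scores". Table 3, offered as a draft format, has one effect size per variable for each of the 11 projects and for all projects together, then one for each numbered comparison column and for the comparison group as a whole. It has no column for the net effect.

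Net impact itself is defined in section 4.3(iii) as a comparison of the changes in the two groups. Section 9.2.3 estimates the group difference by structural equation modelling on the combined dataset.

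**The concern.** Applied column by column, the footnote 62 formula gives each column of Table 3 a different yardstick. A project with a more homogeneous intake shows a larger effect size for the same number of points gained. Children develop between the two waves in both arms, so any difference in spread turns shared growth into a difference between columns.

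The size of these figures matters to the protocol. Section 5 targets effects of 0.2 to 0.5, section 9.2.2 wants results comparable with other early years programmes, and section 11 treats effects near 0.3 as lasting and those below 0.2 as fading. Unequal spread is possible: section 5.2 says the areas can be matched on deprivation score but not on other family characteristics, and section 9.1.1 allows for systematic variation between the groups and within the treatment group.

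**Working it through.** **The plan's own figure.** For an effect of 0.8, the standard normal distribution function gives Φ(0.8) = 0.788, which is the 79% in footnote 62. The example therefore reads the effect against the baseline distribution of the group being scored.

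**Inputs from the protocol.** 35 children per project and 385 per group (sections 4.5 and 5); target effect 0.2 to 0.5 (section 5).

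**Assumed inputs.** The protocol gives no SDs, growth rates or pre-post correlations. Let both columns have the same raw growth g, measured in units of the comparison column's SD, and let k be the project SD divided by the comparison SD. The true net impact is zero.

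**Gap between columns.** Project entry = g/k; comparison entry = g; gap = g/k − g.

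| g | k = 0.9 | k = 0.8 |
|---|---|---|
| 0.3 | 0.033 | 0.075 |
| 0.6 | 0.067 | 0.150 |
| 1.0 | 0.111 | 0.250 |

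At g = 0.2 and k = 0.8 the gap is only 0.05. If the project is the more variable column the sign reverses: g = 0.5 and k = 1.25 gives 0.40 − 0.50 = −0.10. A gap of 0.2 needs k = g/(g + 0.2), which is 0.71 at g = 0.5 and 0.80 at g = 0.8.

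**Chance differences in SD, equal true spread.** With 35 children and an assumed pre-post correlation of 0.6, the coefficient of variation of the pooled SD is 0.5 × √((1 + 0.6²)/34) = 0.10. In simulation with correlations of 0.5 to 0.7, the ratio of two columns' SDs had a 95% range of about 0.75 to 1.34 at 35 per column, and about 0.92 to 1.09 at 385. In the All columns at g = 0.6, the lower extreme gives 0.6/0.92 − 0.6 = 0.05.

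**How much of this is only noise.** With 35 per column and correlation 0.6, the difference between two columns' mean changes has a standard error of √(2 × 2 × 0.4/35) = 0.21. A 10% error in each SD adds 0.6 × 0.10 × √2 = 0.085 at g = 0.6. Combined: √(0.214² + 0.085²) = 0.23, about 8% more.

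**Effect of a common SD.** Take g = 0.8 and k = 0.8. With own-column SDs the entries are 1.00 and 0.80, a gap of 0.20. With one common SD of √((1 + 0.8²)/2) = 0.906, both entries are 0.8/0.906 = 0.883 and the gap is zero. The gap is zero for any k.

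**The case against.** - **Own-column scaling is inferred.** No sentence says outright that each column is divided by its own SD; footnote 62 explains an index while discussing the literature, and Table 3 is a draft. This stands, but it is the natural reading of the formula, the back-reference and the layout together, and nothing points to a common SD.
- **A gap between columns is not the plan's net impact.** A reader might infer that unequal spread would create a false net impact. The documents do not support that. Net impact compares changes (4.3(iii)) and is estimated on the combined dataset (9.2.3); section 9.2.1 recalibrates the latent scores on that dataset; nothing says that Table 3 columns are to be subtracted; and the table's asterisk marks a significance test, not a visible gap. This stands in full.
- **Means and SDs are already promised** in section 9.2.2, so a careful reader could see unequal spread. This stands in part: the Table 3 layout shows only effect sizes.
- **The magnitude is assumed.** This stands. Real differences in spread are needed for a systematic distortion, and the protocol gives no evidence of their size. Chance error in the SD adds modestly to noise that is already large at 35 per column, and a common SD would not cure that noise. The growth argument also applies mainly to child outcomes, while section 9.2.2 covers parents and staff too.

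**Conclusion.** The point holds as one about the reported size of impacts. With the stated formula applied by column, equal raw change gives unequal effect sizes wherever spreads differ, so Table 3 columns cannot safely be compared in size or ranked. On the assumed values the gap is 0.08, 0.15 or 0.25 for growth of 0.3, 0.6 or 1.0 SD with a project SD 20% lower. It is negligible when growth is small or spreads are similar, and by chance alone it stays at about 0.05 or less in the All columns at growth of 0.6.

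It would go too far to say that the columns can never be compared: where spreads are similar, they can. The structural equation test of net impact, the significance flags and the power do not rest on these denominators. Separately, footnote 62 defines a within-group change where the text it annotates describes a between-group difference. That inconsistency is in the text and needs no assumption.

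**What to change.** In footnote 62 and section 9.2.2:

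1. Standardise every column of Table 3 by one common SD per outcome: the baseline SD pooled within groups over both arms.
2. Report the net effect as the change in the treatment group minus the change in the comparison group, divided by that same SD.
3. Reconcile footnote 62 with the main text of section 4.5, so that the within-group change and the treatment-versus-comparison effect are named and defined separately.

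The means and SDs already promised in section 9.2.2 should sit beside Table 3 so that raw change is visible. The cost is a sentence or two in each place: no new data, no change in sample size, and no change to the modelling.

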The first consideration is the minimum sample size required to ensure that statistical tests are able to detect a difference between the treatment group and the comparison group. This is called the power of a statistical test and the convention is that a sample which allows differences to be detected in 80% of cases (referred to as a power of 0.8) is acceptable. Conversely, this convention accepts the likelihood that differences between the treatment and comparison group may not be detected in 20% of cases.

The second consideration is the level of significance attached to any result produced by a statistical test. The convention here is that results should be true in 95% of cases (referred to as $p=0.05$). Conversely, this convention accepts that differences detected between the treatment and comparison groups may not be true in 5% of cases.

The third consideration is the effect size which is expected as a result of the programme. As explained in the previous section, the impact of a programme is typically expressed in terms of effect sizes and most effective programmes for children and families tend to achieve effect sizes in the range 0.2 to 0.5 across a wide range of outcome domains and this seems to be an appropriate target for the NEYAI (see Appendix One). Based on these considerations, a sample of 35 participants is appropriate for each group, bearing in mind that most of the statistical analysis will be based on the combined samples of treatment group (385 cases) plus comparison group (385 cases), equal to 770 cases. This is a safe sample size by comparison with more celebrated evaluations of early years programmes⁷¹.

70 Request for Tender For Evaluation of National Early Years Access Initiative, 2011:8.

71 One of the more celebrated evaluations of a pre-school programme - High Scope which was first introduced into Perry Elementary School in the Michigan city of Ypsilanti in 1960 and has tracked children from then till age 40 – is based on a combined sample of 123 (58 in the treatment group and 65 in the control group) (Schweinhart, Montie, Xiang, Barnett, Belfield and Nores, 2005). Similarly, the Carolina Abecedarian

The fourth consideration is that in order to undertake multi-level modelling, as we propose, there is a 'rule of thumb' which requires a minimum of 30-35 cases in each individual 'cluster' or project. Multi-level modelling is required in order to accurately estimate the sources of variability in NEYAI outcomes that are attributable to individual-level variables (i.e., differences between individual children and parents – level 1) and group-level variables (i.e., differences between the clusters of childcare centres in each project – level 2). The sample of 35 therefore has built in provision for a drop-out of 5 cases per project, equivalent to an attrition rate of 14%.

The fifth consideration is that the sample of children and parents must be related to each other as a family – hence the term 'children and *their* parents' – since the evaluation needs to assess how NEYAI impacts not only on children and parents as separate individuals but also on both as a family unit, including the separate dynamics within the family as possible mediators of outcomes. The rationale for this has already been spelt out in logic model. This implies that once a child is selected, then the child's parent is automatically selected, and *vice versa*.

